1 STUDY SYNOPSIS

Sponsor- Investigator	[name]. med. [name] Department of General Internal Medicine University Hospital Bern (Inselspital) [name] [contact]
Study Title	Discontinuing Statins in Multimorbid Older Adults without Cardiovascular Disease – a randomized non-inferiority clinical trial
Short Title / Study ID	STREAM
Protocol Version and Date	V2.3, 13.06.2022
Study Registration	ClinicalTrials.gov SNCTP (Swiss National Clinical Trials Portal)
Study Category and Rationale	According to ClinO, Art. 60 & 61, this clinical trial, assessing deprescribing of statin, comes under “Other Clinical Trial”, Risk Category A.
Background and Rationale	Statins are among the most widely used drugs. While they were found to be effective for primary and secondary prevention of cardiovascular disease (CVD) in middle-aged subjects, their benefits for primary prevention in older people (aged ≥70) without CVD are uncertain, particularly for those with multimorbidity. However, statin side effects and drug interactions are common in a multimorbid elderly population and can negatively impact quality of life and increase adverse drug reaction-related hospitalizations. Therefore, we aim to conduct a statin deprescribing randomized controlled trial (RCT) to provide guidance on the long-term benefits and risks for the ever-growing multimorbid elderly population.
Risk / Benefit Assessment	Potential risks of discontinuing statins might include increased CV events. However, current trials found no benefits of statins after 70 years of age for primary prevention. In the multimorbid elderly, statin side effects and drug interactions are common and discontinuing statin might positively impact quality of life.
Objective(s)	The primary objective is to compare a composite endpoint of major CV events and all-cause death between control and intervention group. Secondary objectives are the comparison of patient-centered outcomes between the two groups.
Endpoint(s)	The primary endpoint is a composite endpoint of major CV events (non-fatal myocardial infarction, non-fatal ischemic stroke) and all-cause death over a follow-up period of 2 years. Secondary endpoints are all-cause death, non-CV death, major CV events, coronary and peripheral artery revascularization, EQ-5D questionnaire, verbal numeric pain rating score, falls, SARC-F questionnaire and Girerd Medication adherence scale.
Study Design	The study is a multicenter, randomized, non-inferiority trial conducted in multiple hospitals in Switzerland. The study is open-labelled, with blinded outcome adjudication. Study subjects are randomly assigned in a 1:1 ratio to either discontinue (intervention arm) or continue (control arm) statin therapy.
Statistical Considerations	We hypothesize that discontinuing statins does not result in shorter event-free survival. The non-inferiority margin is set at 5.2 weeks over a two year observation period. To claim non-inferiority, the lower limit of the difference in two-year restricted mean survival time (RMST) between the treatments must be less than the non-inferiority margin in both intention-to-treat and per-protocol analyses. RMST will be calculated using either Stata's strmst2 or R's survRM2 package. Besides RMST, the effect will also be reported on the hazard ratio scale. Interim analyses will compare the proportion of events that occur in the two arms after each 50 events. Of the 50 events, if significantly more than half occur in the experimental arm, the DSMB will be called to an adhoc meeting to discuss closing the trial early. Due to safety concerns in the those under 75, we will use a lower stopping boundary to ensure stopping that arm if there is evidence of a safety issue. Should this boundary be breached, the DSMB will have to decide whether to close the strata (not the trial).

Inclusion- / Exclusion Criteria	
Inclusion criteria:
 
 • ≥70 years of age • Multimorbid with ≥2 coexistent chronic conditions (defined by ICD-10 codes) with an estimated duration of 6 months or more based on clinical decision, besides dyslipidemia treated by statins • Taking a statin for ≥80% of the time during the year before baseline 
Exclusion criteria:
 
 1. Secondary prevention based on previous large statin trials, defined as: 
 • History of myocardial infarction type 1 (NSTEMI/STEMI) OR • History of unstable angina, defined as ACS symptomatic at rest, crescendo or new-onset angina (CCS 2 or 3) without ECG or cardiac biomarker changes (based on available documents) OR • Stable angina pectoris with a documented ischemia on a stress test or with a significant coronary disease defined as a coronary stenosis >50% OR • History of percutaneous coronary intervention (balloon or stent) or coronary artery bypass graft OR • History of ischemic stroke¹ OR • History of Transient Ischemic Attack, defined as transient neurological deficit without diffusion restriction in MRI OR • History of carotid revascularization (stent or bypass) OR • History of peripheral arterial disease requiring revascularization (stent or bypass; Fontaine IV) 2. Aortic disease that required a vascular repair or aortic aneurysm with a maximum diameter >5.5 cm (men) or >5.2 cm (women) based on available documents 3. Diagnosis of familial hypercholesterolemia based on Dutch lipid score ≥6 based on available documents (LDL-c, Family History, Personal History) (1) 4. Elevated risk of death within 3 months after baseline, defined as: 
 • hospitalized patients planned for palliative care within 24h of admission OR • hospitalized patients with a Palliative Performance Scale (PPS) level <30% (based on situation at least 1 month before hospitalization), this corresponds to an estimated survival of 43% after 3 months (2); OR • patients with an advanced metastatic cancer prognosis of ≤20% survival rate within 1 year after baseline (based on an online tool: https://cancersurvivalrates.com) 5. Participation to a clinical trial with potential impact on the STREAM cardiovascular endpoints (based on clinical judgment)
Number of Participants with Rationale	
The target sample size is 1'800 participants, 900 in each group. Assuming an event rate of 34% at 24 months, a 2% dropout rate per year and 85% protocol adherence (based on OPERAM data), 1800 participants should yield 89% power for the ITT analysis and 83% power for the approximated PP analysis at a one sided α of 0.025. Simulations were performed in Stata 15.1 with the strmst2 package for calculating restricted mean survival time.

Study Intervention	
In the intervention group, statin therapy will be stopped from the next scheduled intake after given informed consent onwards. Additional lipid-lowering medication lowering LDL cholesterol (i.e., ezetimibe, PCSK9 inhibitors, future novel lipid-lowering medications with lowering of LDL cholesterol demonstrated in randomized trials) will also be stopped in the intervention group.

Control Intervention	
No control intervention is planned. In the control group, statin therapy will be continued as prescribed before the trial.

Study procedures	
Study inclusion and baseline assessment is performed on-site. Then, outcomes are assessed at three months and afterwards yearly by phone call. In addition, medical records are reviewed to obtain information from hospitals and GPs about medical events and concomitant treatment during the intervention period. Patients are asked for a separate consent for yearly observational data collection after the intervention period up to 10 years after baseline.

Study Duration and Schedule	
The expected recruitment period is 36 months. Study subjects remain in the study for the entire duration of the intervention period. Minimum intervention period duration is 12 months, maximum intervention period duration is expected to be 48 months. After the end of the intervention period, an optional long-term follow-up observation with annual phone calls for a maximum of 10 years from baseline is planned.
 
Planned First-Participant-In: 10/2021 Planned Last-Participant-Out (Intervention period): 10/2026 Planned Last-Participant-Out (Long-term follow-up): 10/2035

¹ This exclusion criterion does not apply to clearly cardio-embolic causes for stroke, (e.g. due to atrial fibrillation)

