5 STATISTICS AND METHODOLOGY

5.1. Non-inferiority margin and sample size calculation

The sample size calculation is based on a non-inferiority design where we test whether discontinuing statins does not result in reduced event-free survival time (primary endpoint) up to a certain degree (non-inferiority margin). The primary effect measure will be the difference of the Restricted Mean event-free Time over 24 months between the two arms (61, 62).

We defined the non-inferiority margin on the absolute scale of integrated risk difference and fixed it at 5% over 24 months of follow-up (63). This can be interpreted as follows: we want to exclude a loss in event-free time of more than 2 ½ weeks per year (or about 1.5 days per month) over a two year observation period (5.2 weeks overall). This difference is considered by the Steering Committee clinically irrelevant (=non-inferiority) given the multimorbid study population with a high event and death risk.

Based on data from our OPERAM trial (59), we calculated the probability of dying from non-cardiac causes at 12 months as 11.6% and the probability for non-fatal and fatal CV events as 9.1%. Simulations with 10,000 runs were used to calculate the sample size. A Weibull distribution was used to simulate event-free survival data (64). Parameters were chosen to account for a flattening of event probabilities over time. Based on the available OPERAM data, the primary event probabilities in the control group at landmark timepoints were as follows: 22% at 12 months, 34% at 24 months, 43% at 36 months; a drop-out rate of 2% over 1 year was observed (59). Sample size calculations were done in Stata (release 15.1) using the *survsim* package for the simulations and the *strmst2* package for calculating Restricted Mean Event-free Time (65). With 1,800 participants, we will achieve a power of 89% in the Intention-To-Treat (ITT) and 83% in the approximated PP analysis set at a one-sided α level=0.025. We performed several sensitivity

analyses assuming higher and lower event rates as well as non-proportional hazards, and power was >80% in all scenarios. The planned interim analysis (see 5.5) will have no relevant influence on the type I and II error rate and therefore, sample size is not adjusted (66).

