5.3 Statistical methods for primary and secondary outcomes

The primary statistical analysis of the trial will be done at CTU Bern based on well-established standard operating procedures, using an appropriate statistical software. Details are specified in a statistical analysis plan, to be written at the start of enrolment and to be finalized before 25% of patients are enrolled. The plan determines all necessary data preparation steps (e.g. additional validations, generation of new variables), definitions (e.g. analysis sets), and statistical analyses (e.g. models, outputs such as tables and graphs).

The primary outcome of the trial is analyzed with a flexible parametric survival model with all stratification factors as covariates. The difference in Restricted Mean Event-free Time over 2 years will be the effect measure (61, 74). Two years was chosen as this is the average follow-up time in the trial and a clinically useful timeframe given the elderly patient population with higher mortality. Two analyses sets are used for the primary analysis as described below. Non-inferiority will be declared, if for both ITT and PP analysis sets, the one-sided 97.5% confidence interval does not cross the non-inferiority margin. We acknowledge that any choice for the non-inferiority

margin is to some extent subjective and a margin that is universally agreeable is not achievable especially in this heterogeneous patient population (75, 76). Therefore, we will also present results for various margins with the respective uncertainty (77). Components of the primary outcome and other time-to-event outcomes are analyzed with the same methods as the primary outcome. Effects on time-to-event outcomes may also be presented as hazard ratios. Continuous outcomes will be analyzed using linear regression with baseline values and stratification factors as covariates and mean difference as effect measure. Given the potentially high mortality rate we will also explore joint modelling of continuous outcomes and death (78).

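### The synopsis states the primary non-inferiority rule with the inequality reversed, against sections 5.1 and 5.3 and the protocol's own power calculation

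*Protocol*

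**What the plan says.** The Statistical Considerations row of the synopsis states: "The non-inferiority margin is set at 5.2 weeks over a two year observation period". It then requires that "the lower limit of the difference in two-year restricted mean survival time (RMST) between the treatments must be less than the non-inferiority margin", in both the intention-to-treat (ITT) and per-protocol (PP) analyses. It gives neither the order of subtraction nor a sign for the margin.

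Section 5.1 defines the margin: "We defined the non-inferiority margin on the absolute scale of integrated risk difference and fixed it at 5% over 24 months of follow-up". It also gives the direction: "we want to exclude a loss in event-free time of more than 2 ½ weeks per year", or 5.2 weeks over the two years.

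Section 5.3 restates the decision rule: "Non-inferiority will be declared, if for both ITT and PP analysis sets, the one-sided 97.5% confidence interval does not cross the non-inferiority margin". It too gives no arm order or sign.

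**The concern.** A loss of more than 5.2 weeks can be excluded in two equivalent ways. If the difference is discontinue minus continue, the lower limit must be greater than -5.2 weeks. If the difference is the loss, continue minus discontinue, the upper limit must be less than +5.2 weeks. The synopsis takes the lower limit from the first form and the less-than sign from the second. With a signed margin, the result is wrong whichever way the difference is taken.

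The sentence governs the trial's main conclusion, that stopping statins is acceptable with respect to death, myocardial infarction and stroke. Among the statements of the rule, it is also the only one that names a limit and a direction of comparison. The most specific statement is therefore the wrong one. A reader who has only the synopsis sees a criterion that a harmful result would satisfy, and the protocol contains two incompatible versions of its primary rule.

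**Working it through.** **Inputs from the protocol.** Control event probabilities are 22%, 34% and 43% at 12, 24 and 36 months, with a Weibull distribution and 2% dropout per year (section 5.1). There are 900 participants per arm, one-sided alpha is 0.025 and adherence is 85% (synopsis). The margin is 5% of 24 months = 1.2 months, or about 5.2 weeks.

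**Assumptions.** Administrative censoring was varied from none to uniform over 12 to 48 months. The PP set was taken as 85% of 900 = 765 per arm.

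**Step 1: standard error.**
- A Weibull through S(12) = 0.78 and S(24) = 0.66 has shape ln(ln 0.66 / ln 0.78) / ln 2 = 0.742. It gives S(36) = 0.570, which matches the stated 43%.
- Control RMST to 24 months is 19.03 months.
- The per-participant variance is v = ∫ A(t)² h(t) / [S(t)G(t)] dt over 0 to 24 months. Here A(t) is the area under S from t to 24, h is the hazard and G is the probability of being uncensored. This gives √v = 8.06 to 8.12 months across the censoring assumptions.
- SE = √(2v/900) = 0.380 to 0.383 months.

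**Step 2: reproduce the stated power** under the rule that the lower limit exceeds -1.2 months.
- ITT: Φ(1.2/0.383 - 1.96) = Φ(1.17) = 88.0%. With SE 0.380 it is 88.5%. The protocol states 89%.
- PP: SE = 0.383 × √(900/765) = 0.415, so Φ(1.2/0.415 - 1.96) = 82.4%. Without censoring it is 83.0%. The protocol states 83%.

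Both agree within about one percentage point.

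**Step 3: probability of meeting each form of the rule, per analysis set.** D is discontinue minus continue, and L is the lower limit, estimate minus 1.96 SE.

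| Rule | True loss 5.2 weeks | No true difference |
|---|---|---|
| Intended: D, L > -1.2 | 1 - Φ(1.96) = 2.5% | 88.0% to 88.5% |
| Literal, D, margin -1.2: L < -1.2 | Φ(1.96) = 97.5% | Φ(1.96 - 1.2/SE) = 11.5% to 12.0% |
| Literal, loss (continue minus discontinue), margin +1.2: L < +1.2 | Φ(1.96) = 97.5% | Φ(1.2/0.383 + 1.96) = Φ(5.09), about 100% |
| Literal, D, margin +1.2 as printed: L < +1.2 | Φ(2.4/0.383 + 1.96) = Φ(8.23), about 100% | Φ(5.09), about 100% |

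No literal version gives power near 89%. Only the first row does.

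Simulation of Kaplan-Meier-based RMST (5,000 runs per setting) agrees. At the margin, the intended rule was met in 2.3% to 2.5% of runs and the literal rule with margin -1.2 in 97.5% to 97.7%. With no difference, the intended rule was met in 88.0% to 88.7%.

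**Step 4: both analyses must pass.** Suppose both ITT and PP sit at the margin. The literal signed rule is then met with probability 0.975² = 95.1% at correlation 0, rising to 97.5% at correlation 1. The intended rule gives at most 2.5%. The protocol does not give the correlation, so the whole range is shown.

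**The case against.** The strongest defence is that the body of the protocol has the rule right. A one-sided interval that runs from L upward avoids the margin only if L lies above it, so section 5.3 yields the intended criterion. Section 5.1 supplies the direction, and the power calculation was evidently built on that criterion. This stands, and it limits the point to the synopsis sentence.

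A second defence is that the margin is printed as a size and described as a loss. Less than the margin could then mean that the largest plausible loss is under 5.2 weeks. That is probably what was meant, but the sentence does not say so. It compares a lower limit of a difference with a margin, and a reader has to supply the rest.

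It is also fair to object that 97.5% is not a single property of the printed text. It is a figure per analysis set and needs the margin signed to match the difference. With the printed unsigned margin and discontinue minus continue, the literal rule is met essentially always. The uniform 12-to-48-month follow-up has a mean of 30 months, whereas section 4.3 expects a mean intervention period of 24 months. This affects the power check and the figure of about 12%, but not the 97.5%.

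**Conclusion.** The synopsis misstates the primary decision rule, and the sentence needs correcting. Taken literally with a matching sign, a true loss equal to the margin would satisfy it 97.5% of the time per analysis set. When both analyses must pass, the figure is about 95% to 97.5%. The intended rule gives at most 2.5%. The joint range rests on an unknown correlation and on both analyses sitting at the margin.

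A reader might infer that the trial has lost type I error control, or that a result on the margin would in practice be declared non-inferior 97.5% of the time. The protocol does not support that. It would happen only if an analyst followed this one clause against sections 5.1 and 5.3 and against the rule behind the stated power. The design, the 1,800 participants and the one-sided alpha of 0.025 are unaffected.

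**What to change.** Replace the synopsis sentence with: *Non-inferiority is claimed only if the lower limit of the one-sided 97.5% confidence interval for the difference in 24-month RMST (discontinue minus continue) is greater than -5.2 weeks in both the ITT and PP analyses.*

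Repeating the arm order and the sign in section 5.3 would help but is optional, because that section is already sound. The cost is one sentence. Sample size, alpha, power and trial conduct do not change.

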Data privacy	
For each enrolled trial participant, an eCRF is maintained, using a dedicated electronic data capturing (EDC) system (Webspirit®). Study-related data of the participants are collected in a coded manner. At each study site, the principal investigators safeguard the confidentiality of participating patients' data and maintain appropriate medical and research records for this trial. No patient information containing identifying data will leave the study site, except for contact information that is entered in a separate built-in module in the database and only accessible by specifically-assigned users. Biological material will be appropriately stored in

	the biobank of the University Hospital Bern, a restricted area only accessible to the authorised personnel.
Ethical consideration	The authorization from the local ECs is collected prior to the commencement of the trial, and all protocol changes or unexpected problems concerning human participants will be reported during the trial.
GCP Statement	This study will be conducted in compliance with the protocol, the current version of the Declaration of Helsinki, the ICH-GCP, the HRA as well as other locally relevant legal and regulatory requirements.

2 BACKGROUND AND RATIONALE

Statins are among the most widely used drugs (3). While they were found to be effective for primary and secondary prevention of cardiovascular disease (CVD) in middle-aged subjects (4-6), their benefits for primary prevention in older people (aged ≥ 70) without cardiovascular disease (CVD) are uncertain, particularly for those with multimorbidity (7).

At present, there is no clear benefit of statins in 70+ on all-cause mortality and CVD in primary prevention. First, no evidence of statin benefit for primary prevention was shown in Randomized Controlled Trials (RCTs). In the PROSPER trial among 5804 older adults aged 70-82 years, there was no benefit of statins on CVD in primary prevention (8). In the ALLHAT-LLT trial, there was even a nonsignificant increase in mortality rate in the pravastatin group (24.5%) compared with the UC group (18.5%) (HR=1.34; 95% CI, 0.98-1.84; P=.07) for adults 75 years and older, and no significant between-group difference in the 65-74 years age group (for all-cause mortality, HR 1.08, 95%CI 0.85-1.37; for CHD rate, HR 0.94, 95%CI 0.58-1.51) (9). In subgroups of 70+ participants, a 2019 meta-analysis of RCTs found no statistically significant benefit of statins in primary prevention of CV events in participants without established CVD aged 70 to 75 years (rate ratio (RR) per 1mmol/l reduction in LDL=0.84, 95% CI 0.70 to 1.01) and ≥ 75 years (RR per 1mmol/l reduction in LDL=0.92, 95% CI 0.73 to 1.16) (10), although results might have been impacted by the unusual adjustment per 1mmol/l (not so randomized) and the unusual inclusion of revascularization in the combined endpoint (11). Second, the majority of older individuals suffer from multimorbidity (defined as ≥ 2 chronic conditions) (12-15), and most large RCTs do not include such multimorbid elderly (16). To this day, no RCT examining the benefits of statins in primary prevention has exclusively recruited multimorbid 70+ participants (17), and 70+ participants are under-represented in most RCTs, including those examining statin benefits for prevention (8, 9, 18-23). However, statin side effects and drug interactions are common in a multimorbid elderly population and can negatively impact quality of life and increase adverse drug reaction-related hospitalizations. The proportion of patients developing myalgia on statins has been shown to be as high as 5-20% in observational studies (24, 25), as older age and polypharmacy are known risk factors for developing muscle problems under statins (26). Furthermore, multimorbid elderly patients with polypharmacy are more likely to experience side effects with statins (e.g. elevated liver enzymes, diabetes, myopathy, rhabdomyolysis) and drug-drug interactions (e.g. antibiotics, antifungals), with the potential consequences of drug toxicity, reduced physical activity, sarcopenia and falls (27, 28). In practice, statins are often discontinued in multimorbid elderly without CVD after side effects (29). Third, LDL and total cholesterol levels do not predict CV risk in 70+ individuals without pre-existing CVD, as shown in a study aiming at improving coronary heart disease (CHD) risk prediction (hazard ratio (HR) of CHD events per LDL-Cholesterol per 10mg/L 1.01, 95% CI 0.98 to 1.04) (30). Fourth, the use of the AGLA Risk Score – the tool most used in Switzerland to evaluate CV risk – is not validated in 70+ individuals, as this tool is based on the PROCAM trial, which only included men aged 36 to 65 years (31). Therefore, the use of this tool in 70+ individuals represent an extrapolation but no definitive CV risk evaluation. In summary, the net clinical benefit of statins for primary prevention in multimorbid 70+ elderly remains unclear, and the effect of multimorbidity might shift the evidence towards favoring no statin treatment.

While there is little data to support prescribing of statins for primary prevention in elderly multimorbid persons, there is even less data as to whether it is safe to discontinue statins in these

individuals. Recent guidelines on the topic are conflicting. AHA/ACC Cholesterol Guidelines from 2018 mentioned that it may be reasonable to stop statin therapy when: *“functional decline (physical or cognitive), multimorbidity, frailty, or reduced life-expectancy limits the potential benefits of statins”* (32), while 2019 ESC/EAS Guidelines for the management of dyslipidaemias stated that *“the use of statin therapy declines with increasing age”* (33). Moreover, a 2018 multidisciplinary expert panel invited by the US National Institute of Aging (NIA) and the National Heart, Lung and Blood Institute (NHLBI) concluded that *“existing data cannot address uncertainties about the benefits and harms of statins for primary cardiovascular prevention in adults aged 75 and older, especially those with comorbidities, frailty, and cognitive impairment”* (34). Those are however expert opinions, not based on data from large RCTs on discontinuing statins. The impact of discontinuing statins has not been evaluated in RCTs so far, except in a single RCT including participants with a short life expectancy (<1 year) that found no difference in CV events and mortality between the groups, but a slightly better quality of life among those who discontinued statins (35). In a retrospective cohort study, elderly participants who discontinued statins for primary prevention were more often admitted to the hospital for a CV event. However, several CVD confounding factors were not measured, all-cause death was not examined, and reasons for statin-discontinuation were not reported (36).

Inappropriate medication prescribing encompasses not only under-treatment but also over-treatment, which is common and particularly problematic in the multimorbid elderly with polypharmacy (37). Therefore, the decision to discontinue a medication should be given the same importance as the assessment to start one and should be based on evidence obtained from RCTs. According to a survey of US Medicare beneficiaries ≥ 65 years, deprescribing (if medically justified) would be well received (38). In fact, 92% said they would stop taking one or more of their drugs if their doctor deemed this possible, and 67% wanted to decrease the number of daily drugs (38). When geriatric experts were asked to prioritize candidate drugs for deprescribing, statins ranked third after benzodiazepines and atypical antipsychotics (39). Similar findings are available for Switzerland: as national coordinators for Switzerland, we participated in a multi-national study that conducted a survey among 2,250 General Practitioners (GPs) from 30 countries. Eighty percent of GPs advised discontinuing statins in the oldest-old (i.e. 80+) who suffered from statin-related side effects and frailty, but did not have established CVD (29). In another ongoing survey, 80% of 300 multimorbid elderly were willing to deprescribe (unpublished data). Yet, RCT data on safety of discontinuing statins are lacking.

Given the uncertainty of statin benefits for CVD primary prevention in the multimorbid elderly and the lack of evidence that statins may be safely discontinued (40), we aim to conduct a statin deprescribing RCT to provide guidance on the long-term benefits and risks for the ever-growing multimorbid elderly population, who has been systematically neglected in RCTs (16, 17, 34).

Coronary artery calcium (CAC) measurement is rapidly increasing in clinical use and is recommended for risk re-classification in some guidelines.(33, 41-43) In addition, traditional risk prediction models perform poorly in multimorbid older adults, and addition of CAC and biomarkers might improve prediction in this population. Older patients in primary prevention with subclinical atherosclerosis or elevated biomarkers associated with CVD risk might benefit from continuing statins to prevent CVD, but this hypothesis has not been tested in RCTs and evidence remains also unclear in most guidelines. To address these questions, in a subsample of the present RCT, we aim to measure CAC and biomarkers at baseline.

According to ClinO, Art. 60 & 61, this clinical trial, assessing deprescribing of statin, comes under “Other Clinical Trial”, Risk Category A.

